17. STATISTICAL CONSIDERATIONS

17.1. Study Endpoints and Analysis Plan

Definition of primary outcome/endpoint:

The primary endpoint is the overall response rate defined as the best response within the first 24 weeks of the start of study therapy using RECIST v. 1.1 that has been confirmed at a subsequent

time point (\geq 4 weeks).

Definition of secondary outcomes/endpoints:

PFS is defined as time from enrollment to time of clinical or radiographic disease progression as defined by RECIST v.1.1 criteria. OS is defined as time from enrollment to time of death from any cause.

Analytic plan for primary objective:

We will estimate the response rate to combination therapy with epacadostat and pembrolizumab using the exact 95% confidence interval based on the binomial distribution.

Analytic plan for secondary and exploratory objectives:

- We will estimate the survival distribution for both PFS and OS endpoints using the Kaplan Meier method. The log rank test will be used to examine differences between survival curves using prognostic markers such as KIT mutation status.
- For correlative studies we will apply either the Fisher's exact test or Wilcoxon rank sum test to examine the correlation between response status and markers for categorical and continuous variables, respectively. Because of the limited sample size, the biomarker data analysis is for exploratory research only.

Sample Size Justification

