The primary endpoint of this trial is the objective response rate defined as the best response within the first 24 weeks of the start of study therapy using RECIST v1.1 criteria, and that has been confirmed at a subsequent time point (≥4 weeks).. We will use a Simon mini-max two-stage design with a target objective response rate of 20%, compared to a historical response rate of 5% with salvage tyrosine kinase inhibitor monotherapy¹⁰, and the probabilities of type I and type II error set at 0.1 and 0.2 respectively. In the first stage, 12 patients will be accrued. If less than 1 patient achieves a response among the initial 12 patients, the study will be declared negative and terminated. If at least 1 patient achieves a response, an additional 9 patients will be accrued to the second stage for a total of 21 evaluable patients. If at least 3 total patients achieve a response, that treatment will be declared positive for attaining the primary endpoint. This study design yields at least 80% power to detect a 20% response rate (compared to the null hypothesis of 5%) at a significance level of 10%. There is a 54% chance of stopping at Stage 1 if the true confirmed response rate is at most 5% (null hypothesis). Accounting for 10% dropout, we will plan to enroll a total of 23 patients.

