17.3. Reporting and Exclusions

All patients included in the study must be assessed for response to treatment, even if there are major protocol treatment deviations or if they are ineligible. Each patient will be assigned one of the following categories: 1) complete response, 2) partial response, 3) stable disease, 4) progressive disease, 5) early death from malignant disease, 6) early death from toxicity, 7) early death because of other cause, or 9) unknown (not assessable, insufficient data).

All of the patients who met the eligibility criteria (with the possible exception of those who received no study medication) will be included in the main analysis of the response rate. Patients in response categories 4-9 will be considered to have a treatment failure (disease progression). Thus, an incorrect treatment schedule or drug administration does not result in exclusion from the analysis of the response rate.

All conclusions should be based on all eligible patients. Sub-analyses may then be performed on the basis of a subset of patients, excluding those for whom major protocol deviations have been identified (e.g., early death due to other reasons, early discontinuation of treatment, major protocol violations, etc.). However, these sub-analyses may not serve as the basis for drawing conclusions concerning treatment efficacy, and the reasons for excluding patients from the analysis should be clearly reported. The 95% confidence intervals should also be provided.

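### Does a 95% interval conflict with a 10% decision rule when the smallest positive result, 3 of 21, has an interval that contains the 5% null?

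*Combined protocol and SAP*

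**What the plan says.** Section 17.1 treats the primary endpoint in two places.

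- Under the analytic plan for the primary objective, the response rate is to be estimated "using the exact 95% confidence interval based on the binomial distribution". No null value, test or success criterion is attached to the interval.
- Under the sample size justification, the design is a Simon minimax two-stage design with a 5% null rate, a 20% target rate and "the probabilities of type I and type II error set at 0.1 and 0.2 respectively". The futility rule is: "If less than 1 patient achieves a response among the initial 12 patients, the study will be declared negative and terminated". The final rule, for 21 evaluable patients, is: "If at least 3 total patients achieve a response, that treatment will be declared positive for attaining the primary endpoint".

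The Protocol Synopsis repeats both parts. Section 17.3 mentions intervals once more, at the end of a paragraph on sub-analyses that may not support efficacy conclusions: "The 95% confidence intervals should also be provided". Nothing in the document comments on how a result of exactly 3/21 would read.

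**The concern.** The only planned interval spends 2.5% in each tail, while the decision rule is one-sided with up to 10%. At the design's own boundary the two appear to disagree: 3/21 is declared positive although the 95% interval includes the rate that the trial is meant to exclude. The part of Section 17.1 headed as the primary analysis names only the interval; the count rule sits in the sample size text.

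If someone took the interval as the criterion, success would in effect require 4/21. Power at a true 20% would then fall from 80.3% to 62.4%, and type I error from 8.0% to 1.9%. The boundary result is also not rare: 3/21 makes up 22% of positive outcomes at a true 20% and 77% of the (few) positive outcomes at a true 5%. A further worry is that an ordinary binomial estimate and interval ignore the stop after stage 1.

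**Working it through.** **Inputs (Section 17.1).** Null rate 5%, target 20%; n1 = 12, stop at 0 responses; 9 more patients, n = 21; positive at 3 or more. All figures take 21 analysed patients, as the rule does.

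**1. Reproduce the design.** With X1 ~ Bin(12, p) and X2 ~ Bin(9, p),

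P(positive) = P(X1=1)·P(X2≥2) + P(X1=2)·P(X2≥1) + P(X1≥3).

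- p = 0.05: 0.3413×0.0712 + 0.0988×0.3698 + 0.0196 = 0.0243 + 0.0365 + 0.0196 = **0.080**.
- p = 0.20: 0.2062×0.5638 + 0.2835×0.8658 + 0.4417 = 0.1162 + 0.2454 + 0.4417 = **0.803**.
- Early stop at 5%: 0.95^12 = **0.540**.

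These agree with the plan's 10% limit, at least 80% power and 54% chance of stopping. A full search returns the same minimax design.

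**2. Planned interval at the boundary.** The Clopper-Pearson lower limit L solves P(Bin(21, L) ≥ x) = 0.025 and the upper limit U solves P(Bin(21, U) ≤ x) = 0.025.

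| Responses | Observed | Exact 95% | Exact 80% | Count rule |
|---|---|---|---|---|
| 2/21 | 9.5% | 1.2% to 30.4% | 2.6% to 23.4% | not positive |
| 3/21 | 14.3% | 3.0% to 36.3% | 5.4% to 29.1% | positive |
| 4/21 | 19.0% | 5.4% to 41.9% | 8.6% to 34.5% | positive |

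Among positive results, only 3/21 has a 95% interval that contains 5%.

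**3. Is the two-stage structure the cause?** Using the two-stage distribution, with the stage 1 stop ranked lowest and then total responses, the 95% interval at 3/21 is 3.1% to 36.7%, which also contains 5%. The cause is the confidence level. The exact two-stage one-sided p-value against 5% is 0.080 at 3/21, between 0.025 and 0.10, and 0.019 at 4/21, below both.

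**4. Is the ordinary 95% interval valid after the interim look?** I summed the probabilities of all outcomes (0/12, or s/21 with s ≥ 1) whose interval contains the true rate. Over true rates from 0.1% to 60%, coverage is never below about 95.3%.

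**5. How often 3/21 occurs.** P(total = 3) = 1246·p³(1−p)^18, where 1246 = 12×36 + 66×9 + 220 counts the ways to reach 3 with at least one response in stage 1.

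- p = 0.20: 0.180 of 0.803 positive results, 22%.
- p = 0.05: 0.062 of 0.080, 77%. This is 6.2% of all trials at that rate.

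**6. Bias of the observed proportion.** Its mean is 3.8% at a true 5% and 19.4% at a true 20%. The unbiased (UMVUE) alternative is 190/1246 = 15.2% against 14.3% at 3/21, and 1140/5859 = 19.5% against 19.0% at 4/21: less than one percentage point in each case.

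**The case for a change.** The best case for a change is that a few sentences written in advance would settle how 3/21 is to be read, whereas the same sentences written after the data might look like choosing a favourable rule over an unfavourable interval. A two-sided 80% interval matches a 10% one-sided level and agrees with the rule at n = 21: 5.4% to 29.1% at 3/21 (5.5% to 29.3% on the two-stage distribution), and a lower limit below 5% at 2/21.

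Some of this stands. No section relates the rule to the interval or calls the interval descriptive, and a reader could be puzzled at that one outcome. But the choice has already been made in advance. The count rule is fixed and names the primary endpoint, and no rival criterion exists, so there is nothing left to choose once the data are in.

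The additions also bring less than they seem to. The 80% interval agrees with the rule only if the denominator is 21; at 3/23, with all 23 planned patients counted, its lower limit is 4.9%. The unbiased estimate moves the result by under one point. Two intervals and two estimates for one proportion in a trial of this size may confuse as much as they clarify, and statisticians differ on whether to show them.

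**Conclusion.** The concern does not call for a change. The arithmetic behind it is right: at 3/21 the exact 95% interval, 3.0% to 36.3%, includes 5%. The inference that the plan leaves the governing criterion open is not, because Section 17.1 and the Synopsis say what count is positive and use the interval only to estimate. A 95% estimation interval beside a one-sided rule at 10% is a common and legitimate pairing, and a lower limit of 3.0% at 3/21 honestly shows how modest the evidence is at the boundary.

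Followed as written, the plan gives a decision with type I error 8.0% and power 80.3%, and an interval with at least its nominal coverage. Labelling the interval as descriptive, or adding an 80% interval, is a reporting preference that an analyst can adopt without amending anything. This conclusion assumes 21 analysed patients and a success decision taken from the count, as Section 17.1 states. Which patients form the denominator under Section 17.3 is a separate question and is not settled here.

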3. BACKGROUND

3.1 Gastrointestinal Stromal Tumors (GIST)

Background on GIST:

Gastrointestinal stromal tumors (GIST) are the most common sarcomas of the digestive tract, with approximately 4,000 to 6,000 new cases diagnosed each year in the United States.¹ The majority of these tumors harbor activating KIT or PDGFR-alpha mutations, making them sensitive to targeted treatment with the tyrosine kinase inhibitor imatinib mesylate.² Imatinib has activity against KIT and PDGFR, and is considered first line therapy for non-operable and metastatic GIST. Treatment with imatinib in GIST leads to disease control in 70-85% of patients (overall response rate of 68.1%, and stable disease in 15.6%), with a median progression free survival (PFS) of 20-26 months.³⁻⁶ While targeted therapy with imatinib has significantly improved survival for patients with advanced GIST, about 14% of patients exhibit primary resistance to imatinib.⁴ In addition, the majority of patients will eventually acquire mutations in KIT or PDGFR leading to secondary resistance after an average of 2 years of initial imatinib therapy.⁷⁻⁹

Treatment for imatinib-refractory advanced GIST:

Effective treatment options for patients with imatinib-refractory GIST are limited. Sunitinib, an oral receptor tyrosine kinase inhibitor with activity against KIT, PDGFR, as well as VEGF receptors, FLT3, and RET, has been shown to improve progression free survival in patients with inoperable GIST who have failed imatinib therapy, and is now considered standard second-line treatment for advanced GIST. In a phase III randomized placebo-controlled study of sunitinib versus placebo in patients with imatinib-resistant advanced GIST, the sunitinib group had an overall median progression free survival of 27.3 weeks compared to 6.4 weeks in the placebo group. However, the overall response rate was only 7 percent in the sunitinib treated group, compared with 0 percent in the placebo group. Regorafenib, an oral multikinase inhibitor of KIT, PDGFR, VEGFR, RET, BRAF, and FGFR, has been studied as third line treatment in imatinib and sunitinib refractory patients, and has been shown to improve progression free survival from

0.9 months to 4.8 months (p < 0.0001), with an overall response rate of 4.5 percent. Given the overall low response rates to TKI therapy in the second-line setting and beyond, more effective therapies for imatinib-refractory GIST patients are needed.

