Other TKIs with preclinical activity against KIT and PDGFR have been examined as potential therapeutic options both in front-line and refractory GIST. Dasatinib is a TKI with a spectrum of activity including the SRC family of kinases in addition to KIT and PDGFR that has been evaluated as a treatment option for GIST. Preclinical data has described activity of dasatinib toward mutant KIT, ¹² as well as anti-tumor efficacy in imatinib-resistant GIST cell lines. ¹³ Trent and colleagues presented the results of a phase II study of dasatinib as third-line therapy for GIST at ASCO 2011. ¹⁴ Results included a Choi partial response rate of 32%, a median PFS of 2 months and median OS of 19 months, and a PFS rate of 21% at 6 months.

In summary, although treatment of GIST with tyrosine kinase inhibitors results in demonstrated clinical benefit, this efficacy is not sustained and treatment with KIT inhibition does not result in the cure of patients with advanced disease. Given the overall low response rates to TKI therapy in the second-line setting and beyond, novel and more effective therapies for imatinib-refractory GIST are needed.

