5. STUDY DESIGN

5.1 General study design

This is a single-arm Phase 2 study to evaluate the efficacy of combined epacadostat and pembrolizumab in advanced imatinib-refractory GIST patients.

Study Intervention: All subjects will receive pembrolizumab 200 mg IV every 3 weeks and epacadostat 100 mg PO BID continuously.

Schedule of Evaluations: Subjects will have regularly scheduled study visits at the clinical site on Day 1 of every cycle (CXD1), where safety assessments, including laboratory assessments, vital signs, and physical examinations will be performed (see Section 12 for detailed study evaluations, and Section 13 for study calendar).

Response to treatment will be determined by CT scans of the chest, abdomen, and pelvis with contrast. The overall response rate for the primary endpoint evaluation will be determined by RECIST v1.1 criteria; however, clinical decision making may be made based on immune related RECIST (irRECIST) criteria to allow treatment beyond initial progression (see section 15). In patients who are unable to get a CT scan w/ contrast due to renal function (or any other reason), an MRI with and without contrast may be used instead. Imaging will be performed at the following time points:

Baseline scan	Baseline scan within 4 weeks prior to first treatment
Weeks 1 – 24	Every 6 weeks +/- 1 week (at weeks 6, 12, 18, 24)
Weeks 25 – until disease	Every 12 weeks +/- 1 week (at weeks 36, 48, 60, 72, 84, 96, 108)
progression	
2 years	If subjects achieve ongoing disease control at 2 years, patients will be taken off study treatment and observed with imaging every 12 weeks +/- 2 weeks. If the patient develops disease progression, the option of reinitiating study therapy may be considered.

Version Date: 11/09/2017

Duration of treatment: Subjects will continue treatment until confirmed radiographic disease progression, intolerable toxicity or side effects (see Section 6.6 for Criteria for Withdrawal) or ongoing disease control at 2 years. In the latter case, imaging will be performed every 12 weeks, and should the patient develop evidence of disease progression, the option of reinitiating study therapy may be considered based upon discussion with the study principal investigator.

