6. SUBJECTS SELECTION AND WITHDRAWAL

6.1. Inclusion Criteria

The following criteria are required for inclusion in the study:

- 1. Histologically confirmed diagnosis of GIST.
- 2. Unresectable or metastatic GIST.
- 3. Allowable prior therapies:

Version Date: 11/09/2017

- a. Subjects must have had clinical or radiographic progression on imatinib. Those who were taken off of imatinib for intolerance must have progressed on at least one other TKI.
- b. Subjects must have received ≥ 1 prior systemic therapy (including imatinib). A maximum of 4 prior therapies for metastatic disease are allowed.
- 4. Male or female subjects, age 18 years or older.
- 5. ECOG performance status ≤ 1 (Appendix A)
- 6. Life expectance of ≥ 3 months.
- 7. Laboratory parameters within the following Protocol-defined range. All screening laboratory tests should be performed within 28 days of treatment initiation and must be independent of hematopoietic growth factor support.
 - Absolute neutrophil count $\geq 1.5 \times 10^9/L$.
 - Platelets $\geq 100 \times 10^9/L$.
 - Hemoglobin ≥ 9 g/dL (transfusion is acceptable to meet this criteria)
 - Serum creatinine ≤ 1.5 x institutional upper limit of normal (ULN) OR calculated creatinine clearance ≥ 50 mL/min for subjects with creatinine levels ≥ 1.5 x institutional LH N
 - Aspartate aminotransferase, alanine aminotransferase, alkaline phosphatase $\leq 2.5 \text{ x}$ ULN, or $\leq 5 \text{ x}$ ULN in subjects with liver metastases.
 - Total bilirubin < 1.5 x ULN
 - Note: patients with hyperbilirubinemia clinically consistent with an inherited disorder of bilirubin metabolism (eg, Gilbert syndrome) will be eligible at the discretion of the principal investigator.
 - International normalized ratio (INR) or prothrombin time (PT) < 1.5x ULN unless subject is receiving anticoagulation therapy as long as PT or INR is within therapeutic range of intended use of anticoagulant.
 - Activated partial thromboplastin time (aPTT) < 1.5 x ULN unless subject is receiving anticoagulant therapy, as long as PTT is within therapeutic range of intended use of anticoagulants.

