12.2.2. Assessment for Serotonin syndrome

Subjects will be assessed for the presence of any of the following symptoms (Table 8) of serotonin syndrome at the time points indicated in the study calendar.

Table 8: Symptoms of Serotonin Syndrome

V 1
Tremor and hyper-reflexia
Spontaneous clonus
Muscle rigidity, temperature > 38 C, and either ocular clonus or inducible clonus
Ocular clonus and either agitation or diaphoresis
Inducible clonus and either agitation or diaphoresis

12.2.3. General laboratory assessment.

See Table 11 and 12 for detailed laboratory tests and timing of these tests.

12.2.4. Schedule of Disease monitoring.

A CT scan of the chest, abdomen, and pelvis with contrast will be obtained to evaluate disease status. A scan will be obtained at baseline (within 28 days of first study drug dose), then every 6 weeks for the first 24 weeks (imaging of the area with known disease involvement only (ex: CT chest only or CT abdomen/ pelvis only) is allowed for week 6 and week 18 tumor assessments at the investigator's discretion)). After week 24, a CT chest, abdomen, pelvis with contrast will be performed every 12 weeks until disease progression, withdrawal from study, or ongoing disease control at 2 years (defined as at least stable disease at this point). For patients who achieve ongoing disease control at 2 years, treatment will be stopped and subjects will be observed with a CT scan every 12 weeks. If the patient develops disease progression during this observation time, they will have the option of restarting study treatment at that time.

Table 9: Schedule of Disease Monitoring.

	_
Baseline scan	Baseline scan within 4 weeks prior to first treatment
Weeks 1 – 24	Every 6 weeks +/- 1 week (at weeks 6, 12, 18, 24)
Weeks 25 – until disease	Every 12 weeks +/- 1 week (at weeks 36, 48, 60, 72, 84, 96,
progression	108)

Columbia University Medical Center Herbert Irving Comprehensive Cancer Center Version Date: 11/09/2017

2 years	If subjects achieve ongoing disease control at 2 years, patients
	will be taken off study treatment and observed with imaging
	every 12 weeks +/- 2 week. If the patient develops disease
	progression, the option of re-initiating study therapy may be
	agneidared

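### Scans widen from 6-weekly to 12-weekly after week 24, so the planned Kaplan-Meier PFS is biased upward, by an amount that depends on where the true median lies

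*Combined protocol and SAP*

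**What the plan says.** PFS is the first-listed secondary objective (section 2.2). On analysis, section 17.1 states: "We will estimate the survival distribution for both PFS and OS endpoints using the Kaplan Meier method". Neither 15.7 nor 17.1 names an interval-censored method, a fixed-time PFS rate or a sensitivity analysis for PFS.

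The scan schedule (sections 5.1 and 12.2.4, and the study calendar in section 13) is every 6 weeks, at weeks 6, 12, 18 and 24. Then: "After week 24, a CT chest, abdomen, pelvis with contrast will be performed every 12 weeks until disease progression". The next planned scan after week 24 is therefore at week 36. Sections 8.7 and 15.5 date confirmed progression at the first scan that showed it.

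The protocol assumes no median PFS for this trial. Its background cites three historical figures:

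- Sunitinib after imatinib: "the sunitinib group had an overall median progression free survival of 27.3 weeks compared to 6.4 weeks in the placebo group".
- Regorafenib in third line, where PFS improved from "0.9 months to 4.8 months (p < 0.0001), with an overall response rate of 4.5 percent".
- Dasatinib in third line: "a median PFS of 2 months and median OS of 19 months".

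On prior treatment, section 6.1 says: "A maximum of 4 prior therapies for metastatic disease are allowed".

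**The concern.** Kaplan-Meier takes the recorded date as the event date. A progression that happens at week 26 and is first seen on the planned scan is recorded at week 36. If every event is found at a scan, the curve is flat from week 24 to week 36 and then drops. The error runs in one direction only, towards longer PFS, and the possible delay doubles from 6 to 12 weeks after week 24.

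One of the cited medians, 27.3 weeks, lies in the first 12-week gap. With no control arm on the same schedule, nothing inside the trial offsets the delay. What is at stake is how accurately a secondary endpoint describes this trial's own PFS. The go/no-go decision does not depend on it.

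**Working it through.** **Plan's own figures.** The documents give no median, precision or power for PFS, so there is no PFS figure to reproduce. The only design calculation is the Simon two-stage design for response. It reproduces: type I error 0.080, power 0.803, early stopping probability under 5% of 0.540. Nothing below affects it, because the primary endpoint uses the first 24 weeks only.

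**Inputs.** Scan weeks 6, 12, 18, 24, 36, 48 and so on (section 5.1). Cited medians of 27.3 weeks, 4.8 months and 2 months (section 3.1). At 365.25/12/7 = 4.348 weeks per month, these are 27.3, 20.9 and 8.7 weeks. Enrolled n = 23 (section 17.1).

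**Assumptions not in the documents.** Exponential PFS with S(t) = 0.5^(t/m), where m is the true median. Scans on their nominal weeks, enrolment taken as treatment start, and no dropout. The share of events dated off the scan grid is unknown and is varied below.

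**Step 1: large-sample median, all events at scans.** The Kaplan-Meier median is the first scan week with S at or below 0.5.

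- m = 27.3: S(24) = 0.544, S(30) = 0.467, S(36) = 0.401. The median is 36 under the plan and 30 with 6-weekly scans throughout. The excess is 36 − 27.3 = 8.7 weeks, made up of 30 − 27.3 = 2.7 weeks of ordinary scan lag and 36 − 30 = 6 weeks from the wider interval.
- m = 20.9: S(18) = 0.550, S(24) = 0.451. The median is 24 under both schedules.
- m = 8.7: the median is 12 under both schedules.

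For true medians up to 36 weeks, the wider interval moves the large-sample median only when the true median is between 24 and 30 weeks.

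**Step 2: spread with n = 23, all events at scans.** The median is the 12th ordered time, so P(median ≤ s) = P(Bin(23, 1 − S(s)) ≥ 12). At m = 27.3:

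- s = 24: 1 − 0.544 = 0.456, giving 0.336.
- s = 36: 1 − 0.401 = 0.599, giving 0.834.
- Exactly week 36: 0.834 − 0.336 = 0.498. Later than week 36: 1 − 0.834 = 0.166.

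**Step 3: mean Kaplan-Meier median in weeks, by simulation, n = 23, all events at scans.**

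| True median | Exact dates | 6-weekly throughout | As planned | Added by the interval change |
|---|---|---|---|---|
| 27.3 | 28.2 | 31.2 | 33.7 | about 2.5 |
| 20.9 | 21.6 | 24.6 | 26.0 | about 1.4 |

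The exact-date mean exceeds the true median (28.2 − 27.3 = 0.9) because the sample median of a skewed distribution is itself biased upward in small samples. At a true median of 8.7 weeks the interval change adds nothing.

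**Step 4: events found off the scan grid, m = 27.3.** If 30% of progressions are found clinically at the 3-weekly visits, the mean reported median is about 32.4 weeks. At 50% it is about 31.5. If off-scan events are dated exactly, the large-sample median stays at 36 with up to 30% off-scan, and is 32.9 at 40% and 30.9 at 50%.

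**Step 5: alternatives on the same data, m = 27.3, all events at scans.** At week 24 the expected Kaplan-Meier value equals the true S(24) = 0.544, so the week-24 rate carries no scan-lag bias. Just before week 36 the curve still reads 0.544, against a true value of about 0.40. A Turnbull estimate, interpolated linearly within the gap, has a mean median of about 28.4 weeks, close to the 28.2 obtained with exact dates.

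**The case against.** The case against is substantial. PFS is secondary and is not tested against any historical value. The historical comparison in 17.1 is on response, and the log-rank test there compares marker groups within the trial. Only one of the three cited medians falls in the 24-36 week gap. It comes from a trial after imatinib failure, whereas this trial admits up to four prior therapies. PFS also counts clinical progression (synopsis, 17.1) and death (synopsis, 15.7). Visits are every 3 weeks, unscheduled visits are allowed, and stopping without confirmed progression prompts a scan. Sampling error is larger than the bias: even with exact dates, the central 95% range of the n = 23 median is about 14.5 to 46.5 weeks at a true median of 27.3.

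All of this limits the size of the problem, and three stronger readings fail because of it:

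- A reader might infer that the median is pushed to week 36 by construction. It is not. That needs a true median in the gap and mostly scan-dated events, and even then about a third of trials give week 24 or earlier.
- A reader might attribute the whole 8.7-week large-sample excess to the wider interval. Of this, 2.7 weeks would occur with 6-weekly scans as well.
- A reader might infer that a regimen no better than sunitinib would look better purely because of the schedule. The documents do not give the sunitinib trial's scan schedule or dating rule, so bias relative to the cited 27.3 weeks cannot be computed.

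The objections do not remove the bias. Off-scan events dilute it without reversing it. It is systematic, so unlike sampling error it is not reflected in the width of the Kaplan-Meier interval.

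**Conclusion.** The concern holds in a limited form. Kaplan-Meier on scan-dated progressions overstates this trial's own PFS, and the change to 12-weekly scans increases the overstatement where the true median lies in or near the 24-36 week gap. At a true median of 27.3 weeks with all events at scans, the mean reported median is about 5.5 weeks above the exact-date value (33.7 − 28.2). About 3.0 weeks of that is ordinary scan lag (31.2 − 28.2) and about 2.5 weeks comes from the interval change. With 30% to 50% of progressions found clinically, the total falls to roughly 3 to 4 weeks. These sizes rest on the exponential assumption, nominal scan dates, no dropout and an assumed off-scan share. The direction does not depend on the exponential form. The point is worth correcting because it is cheap, but it leaves the primary conclusion untouched.

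**What to change.** In section 17.1:

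1. Keep the Kaplan-Meier curve and median.
2. Pre-specify the week-24 PFS rate with its 95% CI as a key PFS summary, because the scan interval is constant up to that point. State that a week-24 scan done within its ±1 week window belongs to that assessment.
3. Add a Turnbull interval-censored analysis using the dates of the last progression-free assessment and the first assessment showing progression. Clinical progressions and deaths enter at their own dates.
4. If the Kaplan-Meier median falls at the week-36 scan, report the 24-36 week bracket beside it.

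The text should not state that every median between weeks 24 and 36 will be read as week 36. Off-scan events make that untrue as a general rule.

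The cost is a few sentences and one extra analysis of dates already collected. It needs no extra scans and no change to patient care. There are two downsides. The reported median may look slightly less favourable, and Turnbull brackets the median within the gap instead of locating it, so any single value there depends on interpolation. Both are easier to accept if written down before results are seen.
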